## 2. LIST OF ABBREVIATIONS

AIDS	Acquired immunodeficiency syndrome
ART	Antiretroviral therapy
BCHD	Baltimore City Health Department
ED	Emergency department
HCV	Hepatitis C virus
HIV	Human immunodeficiency virus
ICV	Integrated care van
JHU	Johns Hopkins University
MOUD	Medication for opioid use disorder
PrEP	Pre-exposure prophylaxis
PWID	People who inject drugs
SSP	Syringe service program
STI	Sexually transmitted infection

### 3. PROTOCOL SUMMARY

#### Building on Needle Exchange to Optimize Prevention and Treatment

**Purpose:**

Biomedical interventions that have direct applicability to people who inject drugs (PWID) have flourished over the past 15 years (HIV treatment as prevention, pre-exposure prophylaxis [PrEP], office-based medication for opioid use disorder [MOUD] with buprenorphine, and hepatitis C virus [HCV] treatment with direct acting agents). However, penetration of these interventions among PWID is low relative to the potential benefits. Syringe service programs (SSP) are an essential risk reduction service for PWID, and represent a potential, although under-used, interface to provide additional PWID services. The Baltimore City Health Department (BCHD) and investigators at Johns Hopkins University (JHU) have developed a dedicated integrated care van (ICV) to complement the city's mobile SSP, with the goal of extending needed biomedical interventions to PWID. The primary purpose of this trial is to determine if the ICV intervention reduces risk, improves health, and increases uptake of evidence-based services among PWID. Secondary purposes are to examine the ICV implementation, acceptability, coverage, and sustainability using a mixed methods approach, and to assess costs and cost-effectiveness.

**Design:**

Matched-pair cluster randomized trial.

**Study Population:**

PWID who are 18 years of age or older.

**Study Size:**

The study will be conducted at 12 neighborhood sites or clusters in Baltimore that are visited by the SSP. We aim to enroll 60 participants at each site (720 participants overall).

**Treatment Regimen:**

In addition to continuing weekly visits from the mobile SSP, sites assigned to the intervention will receive weekly visits by the ICV. Staffed by 1-2 medical providers, a case manager, and phlebotomist, the ICV will provide a spectrum of PWID services (e.g., rapid HIV and HCV testing, naloxone overdose kits, HIV treatment and linkage, HCV treatment and linkage, buprenorphine-based MOUD, and PrEP). The ICV will visit neighborhood sites once a week and offer services to anyone seeking them, irrespective of enrollment in the study cohort

Sites assigned to usual care will continue to receive weekly visits from the mobile SSP, but no additional services.

**Study Duration:**

The study duration will be approximately 36 months. Site selection and preparatory work will take 8 months. Participants will be enrolled by site, in staggered fashion, over 14

months, and followed for an additional 14 months.

**Primary Objective:**

To determine if the ICV intervention increases uptake of evidence-based services, reduces risk behaviors, and reduces adverse outcomes among PWID (assessed by a composite PWID score), compared with the control condition.

**Secondary Objectives:**

- To determine if the ICV intervention improves the HIV care continuum (among HIV-positive participants), compared with the control condition
- To determine if the ICV intervention increases HIV testing rates (among HIV-negative participants), compared with the control condition.
- To determine if the ICV intervention improves the PrEP continuum (among HIV-negative participants), compared with the control condition.
- To determine if the ICV intervention improves the HCV care continuum (among HCV-positive participants), compared with the control condition.
- To determine if the ICV intervention increases HCV testing rates (among HCV-negative participants), compared with the control condition.
- To determine if the ICV intervention increases use of MOUD (among all participants), compared with the control condition.
- To determine if the ICV intervention increases use of SSP (among all participants), compared with the control condition.
- To determine if the ICV intervention increases possession of a naloxone overdose kit (among all participants), compared with the control condition.
- To determine if the ICV intervention reduces injection drug use (among all participants), compared with the control condition.
- To determine if the ICV intervention reduces recent drug use (among all participants), compared with the control condition.
- To determine if the ICV intervention reduces sharing of drug paraphernalia (among all participants), compared with the control condition.
- To determine if the ICV intervention reduces non-fatal drug overdoses (among all participants), compared with the control condition.
- To determine if the ICV intervention reduces emergency department use (among all participants), compared with the control condition.

- To determine if the ICV intervention reduces HIV seroconversion (among HIV-negative participants), compared with the control condition.
- To determine if the ICV intervention reduces HCV seroconversion (among HCV-negative participants), compared with the control condition.
- To determine if the ICV intervention decreases mortality (among all participants), compared with the control condition.
- To describe and characterize service utilization on the ICV including, but not limited to, number of visits and unique clients served, client demographics, use of individual services (HIV testing, HCV testing, PrEP, buprenorphine-based MOUD, etc.), and overlap between ICV clients and the neighborhood PWID cohorts enrolled for the study.

[figure not shown]
**Exploratory Objectives:**

- To conduct a qualitative evaluation of barriers to service delivery for PWID, perceptions about the ICV, interest in services provided by and not provided by the ICV, and sustainability of the ICV from in-depth interviews with SSP, ICV staff, and PWID; and by key-informant interviews with policy stakeholders.
- To evaluate ICV cost and assess the potential cost-effectiveness of the ICV as a service delivery modality for PWID.

**Study Sites:**

The study will be conducted at 12 neighborhood locations (cross streets) where the Baltimore City mobile SSP provides clean needles and syringes

## Overview of Study Design and Randomization Scheme:

## 4. INTRODUCTION

### 4.1 Background Information

Since the introduction of combination antiretroviral therapy (ART), studies (including many from our team) have consistently identified barriers and lower access to ART among PWID compared with other HIV risk groups. While active substance use is a well-established barrier to adherence, it is also clear that clinicians often believe PWID are incapable of taking ART. Despite dramatic strides in treating HIV-positive persons overall, PWID disparities remain. A large consortium of HIV cohorts in North America recently found that (compared with other risk groups) PWID were significantly less likely to initiate ART and to achieve viral suppression at 6- and 12-months after reaching guideline-eligibility for ART. Strikingly, female PWID were 36% less likely (95% CI: 25%, 46%) to initiate ART when eligible than MSM. In another study by the NA ACCORD, of all factors assessed, PWID had the strongest association with non-retention to HIV care (68% increased risk of non-retention; 95% CI: 49%, 89%) compared with non-PWID. This pattern has emerged again with pre-exposure prophylaxis (PrEP) and hepatitis C virus (HCV) treatment. In a systematic review, PWID expressed similar levels of PrEP interest as other risk groups; however a survey study found that primary care providers were significantly less willing to provide PrEP for PWID compared to all other risk groups. In a PubMed search we combined the term “pre-exposure prophylaxis” with “MSM” or “men who have sex with men” and identified 373 published articles. In contrast when we combined “pre-exposure prophylaxis” with “PWID” or “people who inject drugs,” only 34 published articles were identified. Tellingly, of the 34 articles, only 2 manuscripts reported actual implementation of PrEP among PWID, both from the Bangkok Tenofovir Study. Finally, unpublished data by our group from the ALIVE study – a community-based cohort of PWID in Baltimore – found that among 269 HCV-positive participants enrolled in 2016-17, less than 10% reported linkage to HCV care and only 3% reported HCV treatment with cure. ***These data highlight the persistent pattern of disparities in access to evidence-based biomedical services by PWID.***

### 4.2 Rationale

A substantial body of literature supports the feasibility, acceptability, and efficacy of models in which substance use treatment and medical management are integrated in a single venue. One small trial from over 20 years ago makes this simple point clearly: 51 methadone clients who had an untreated medical condition were randomized to either on-site treatment at the methadone clinic or referral to a nearby medical clinic, with treatment costs covered by the study. 76% assigned to integrated care attended  $\geq 2$  medical visits compared with 6% referred off-site ( $P<0.001$ ). Other randomized controlled trials, including work by our group, have found that integration of medication for opioid use disorder (MOUD) within general medical or HIV specialty clinics was associated with higher patient satisfaction, increased retention to medical and substance abuse treatment, and higher rates of negative urine drug tests, compared with separate models of care. Pioneering work by Altice and colleagues has shown that a mobile health platform is acceptable, feasible, and effective for serving PWID populations, including vaccination, screening and treatment of latent tuberculosis, buprenorphine-based MOUD, HCV screening, and ART facilitation for HIV-positive persons. ***We propose to build on the prior work of our team and others to implement and evaluate a PWID-focused multi-service van to bring needed biomedical services to this***

*population.*

#### **4.3 Study Hypotheses**

We hypothesize that a multi-service ICV will reduce risk behaviors, improve health, and increase uptake of evidence-based services among PWID.

### **5. OBJECTIVES**

#### **5.1 Primary Objective:**

To determine if the ICV intervention increases uptake of evidence-based services, reduces risk behaviors, and reduces adverse outcomes among PWID (assessed by a composite PWID score), compared with the control condition.

#### **5.2 Secondary Objectives:**

- To determine if the ICV intervention improves the HIV care continuum (among HIV-positive participants), compared with the control condition
- To determine if the ICV intervention increases HIV testing rates (among HIV-negative participants), compared with the control condition.
- To determine if the ICV intervention improves the PrEP continuum (among HIV-negative participants), compared with the control condition.
- To determine if the ICV intervention improves the HCV care continuum (among HCV-positive participants), compared with the control condition.
- To determine if the ICV intervention increases HCV testing rates (among HCV-negative participants), compared with the control condition.
- To determine if the ICV intervention increases use of MOUD (among all participants), compared with the control condition.
- To determine if the ICV intervention increases use of SSP (among all participants), compared with the control condition.
- To determine if the ICV intervention increases possession of a naloxone overdose kit (among all participants), compared with the control condition.
- To determine if the ICV intervention reduces injection drug use (among all participants), compared with the control condition.
- To determine if the ICV intervention reduces recent drug use (among all participants), compared with the control condition.
- To determine if the ICV intervention reduces sharing of drug paraphernalia (among all participants), compared with the control condition.

- To determine if the ICV intervention reduces non-fatal drug overdoses (among all participants), compared with the control condition.
- To determine if the ICV intervention reduces emergency department use (among all participants), compared with the control condition.
- To determine if the ICV intervention reduces HIV seroconversion (among HIV-negative participants), compared with the control condition.
- To determine if the ICV intervention reduces HCV seroconversion (among HCV-negative participants), compared with the control condition.
- To determine if the ICV intervention decreases mortality (among all participants), compared with the control condition.
- To describe and characterize service utilization on the ICV including, but not limited to, number of visits and unique clients served, client demographics, use of individual services (HIV testing, HCV testing, PrEP, buprenorphine-based MOUD, etc.), and overlap between ICV clients and the neighborhood PWID cohorts enrolled for the study.

### **5.3 Exploratory Objectives:**

- To conduct a qualitative evaluation of barriers to service delivery for PWID, perceptions about the ICV, interest in services provided by and not provided by the ICV, and sustainability of the ICV from in-depth interviews with SSP, ICV staff, and PWID; and by key-informant interviews with policy stakeholders.
- To evaluate ICV cost and assess the potential cost-effectiveness of the ICV as a service delivery modality for PWID.

## **6. STUDY DESIGN**

This is a comparative effectiveness, two-arm, matched-pair cluster randomized trial. The study will be conducted in 12 neighborhood sites in Baltimore City that receive services from the mobile SSP. Eligible PWID will be recruited at each site prior to randomization. In each site pair, one site will be assigned to the control condition and the other site to the ICV intervention.

1. Control condition – Sites assigned to usual care will continue to receive weekly visits from the mobile SSP, but no additional services.
2. Intervention – In addition to continuing weekly visits from the mobile SSP, sites assigned to the intervention will receive weekly visits by the ICV. Staffed by a medical provider, nurse, and phlebotomist, the ICV will provide a spectrum of PWID services (e.g., rapid HIV and HCV testing, naloxone overdose kits, HIV treatment and linkage, HCV treatment and linkage, buprenorphine-based MOUD, and PrEP). The ICV will visit neighborhood sites once a week and offer services to anyone seeking them, irrespective of enrollment in the study cohort

In addition to the quantitative endpoints from the trial, we will also collect qualitative

data to understand whether the ICV was recognized by clients and how ICV service provision was perceived by different stakeholders. Additionally, a cost-effectiveness evaluation is planned.

The study duration will be approximately 36 months. Site selection and preparatory work will take 8 months. Participants will be enrolled by site, in staggered fashion, over 14 months, and followed for an additional 14 months.

## 7. STUDY POPULATION

We will recruit cohorts of PWID at each neighborhood site, with roll-out of the study arm allocation (intervention or control condition) near the conclusion of cohort enrollment. Cohort participants will be followed for 14 months during the intervention phase. The exploratory objectives require i) collection of qualitative data from key stakeholders, including PWID, SSP staff, ICV staff, and policymakers, ii) conduct cost-benefit analyses.

### 7.1 Enrollment Criteria

The enrollment criteria were designed to enroll high-risk PWID. To optimize enrollment of HIV-positive individuals, we structured the inclusion criteria so that HIV-positive individuals did not have to be recent injectors. HIV point-of-care rapid testing (with pre- and post-test counseling) will be conducted as part of study screening. An important component of study recruitment (and follow-up) will be the use of biometric identification (iris scans) to prevent duplicate enrollments of participants at different neighborhood sites (and to ensure proper attribution of follow-up visits). We have found this method to be highly acceptable to the target population, rapid (about 20 seconds), accurate, and safe (the program uses a proprietary algorithm to generate a unique, reproducible code from iris images, but does not store photographic images).

#### 7.1.1 *Participant Inclusion Criteria*

##### Inclusion criteria for cohort participants

Men and women who meet all of the following criteria are eligible for inclusion as a cohort participants:

- 18 years of age or older
- Injection drug use history according to HIV status
  - If HIV-negative
    - Injected 4 or more days in the prior 30 days
    - or
    - Shared needles/syringes in the prior 6 months
  - If HIV-positive
    - History of injection drug use

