## 12.7 Analysis Plan

### 12.7.1 *Analysis plan for primary and secondary endpoints*

We will estimate the impact of the ICV on the composite primary outcome which incorporates the following: HIV prevention, testing, and treatment; HCV prevention, testing, and treatment; substance use and treatment; overdose; and healthcare utilization (see Appendix). We will also estimate the impact of the ICV on the separate measures that make up the composite outcome, including the HIV care cascade, the PrEP continuum, MAT engagement, and linkage to HCV treatment. The outcomes will be continuous (composite primary outcome), ordinal (HIV care cascade, PrEP continuum, HCV linkage), and dichotomous (MAT), and the analytic samples will vary depending on

the outcome. For all outcomes, the data will have the same structure, with time ( $t$ ) nested within participants ( $i$ ) nested within SSP sites ( $j$ ). The three-level structure of the data will induce correlations in the outcomes within sites and within participants, and this will be addressed by using random intercepts for site and random intercepts for participants. Fixed effects will include covariates for calendar time (a linear, quadratic, spline terms, or indicators as indicated by exploratory data analysis), indicator for 6-month follow-up assessment, a time-varying indicator for ICV exposure status, and follow-up-by-ICV-status interaction terms. This general linear model can be expressed as:

$$\pi_{ijt} = \beta_0 + U_{0i} + U_{0j} + ICV_{ijt}\beta_1 + FU_{ijt}\beta_2 + ICVxFU_{ijt}\beta_3 + \mathbf{x}'_{ijt}\boldsymbol{\gamma} + \mathbf{z}'_j\boldsymbol{\zeta} + \varepsilon_{ijt}$$

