where:  $\pi_{ijt}$  denotes the linearized expected outcome for participant  $i$  at SSP site  $j$  on occasion  $t$ ;  $\beta_0$  is the overall intercept;  $U_{0i}$  and  $U_{0j}$  are normally distributed person-level and site-level random intercepts;  $ICV_{ijt}$  is an indicator for participation being at an ICV site,  $FU_{ijt}$  is a binary indicator for the 6-month follow-up assessment;  $ICVxFU_{ijt}$  is an ICV-by-follow-up interaction term;  $\mathbf{x}_{ijt}$  is a vector of participant-level covariates with  $\boldsymbol{\gamma}$  the vector of corresponding fixed-effects regression parameters;  $\mathbf{z}'_j$  is a vector of SSP site covariates (including intervention phase) with  $\boldsymbol{\zeta}$  the vector of corresponding fixed effects; and  $\varepsilon_{ijt}$  are error terms. The null hypothesis of no significant group-by-time interaction at the follow-ups can be tested using a 1-df F-test of  $H_0: \beta_3 = \mathbf{0}$ . The form of  $\pi_{ijt}$  and the expected distribution of the residuals will be specified based on the specific outcome. For the composite outcome, we will use mixed effects linear regression with an identity link function and normally distributed residuals.

The above-described model does not have a coefficient for matched-pair, and therefore “breaks the pairing.” This approach may be more statistically powerful when the matching accounts for little variability among clusters, and we expect that to the case given the limited information that was available for conducting the matching. How much variability is accounted for by the matching will be based on reduction in the variance of the cluster-level random intercept when including fixed effects for matched-pairs, and a likelihood ratio test comparing models with and without fixed effects for matched-pairs.

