## 14. APPENDIX

**Table. Rubric for composite PWID score (service access, risk behaviors, adverse outcomes)**

Score component	Denominator	Category definitions
Service access		
HIV care continuum	HIV positive	0 – Suppressed (HIV RNA <200 c/mL) 1 – Not suppressed, and either i) took ARVs in prior 30 days (self-report) OR ii) had visit with HIV provider in prior 6 months 2 – Not suppressed AND did not take ART in prior 30 days AND did not have visit with HIV provider in prior 6 months (includes those unaware of HIV+ status) at the visit
HIV testing	HIV negative	0 – Had HIV test in past 6 months 1 – Did not have HIV test in past 6 months
PrEP continuum	HIV negative	0 – Used PrEP in prior 6 months (self-report) 1 – Did not use PrEP in prior 6 months
HCV care continuum	HCV positive i. all Ab(+) + RNA(+) or ii. Ab(+) + RNA(-) + treated	0 – HCV treatment history (self-report) and HCV RNA suppressed (<15) 1 – Not suppressed and either treated for HCV OR evaluated by HCV provider in prior 6 months 2 - Not suppressed AND not treated for HCV in prior 6 months AND not evaluated by HCV provider in prior 6 months.
HCV testing	HCV negative i. Ab(-) or ii. Ab(+) + RNA(-) + never treated	0 – Had HCV test in past 6 months 1 – Did not have HCV test in past 6 months
MOUD use	All	0 – Used MOUD in past 6 months 1 – Did not use MOUD in past 6 months
SSP use	Injected in prior 6 months	0 – Used SSP in past 6 months 1 – Did not use SSP in past 6 months
Available naloxone kit	All	0 – Has naloxone kit on person or where drugs used 1 – Does not have accessible naloxone kit
Risk behaviors		
Injection drug use	All	0 – No injection drug use in prior 6 months (self-report) 1 – Injection drug use in prior 6 months
Recent drug use	All	0 – Urine drug test negative for drugs of concern (*see footnote) 1 – Urine drug test positive for one or more drugs of concern (*see footnote)
Sharing injecting equipment	All	0 – No sharing syringe/works OR not using/injecting in prior 6 months 1 – Sharing works (cotton/cooker) only in prior 6 months 2 – Sharing needle/syringe in prior 6 months
Adverse outcomes		

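### Entry criteria fix the injecting item at 1 at baseline for nearly all HIV-negative participants, so an arm-by-visit test of that secondary endpoint loses much of its power

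*Combined protocol and SAP*

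**What the plan says.** Section 7.1.1 gives HIV-negative people two ways in: "Injected 4 or more days in the prior 30 days" or "Shared needles/syringes in the prior 6 months". HIV-positive people need only "History of injection drug use", and Section 7.1 explains that this was deliberate: "HIV-positive individuals did not have to be recent injectors".

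The Appendix rubric scores the injecting item 0 or 1 according to "injection drug use in prior 6 months", by self-report, with all participants in the denominator. Sections 5.2 and 12.2.2 make injecting a separate secondary endpoint, also in all participants. Section 9.1 says the baseline visit usually takes place on the day of screening.

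Section 12.7.1 will estimate effects on "the separate measures that make up the composite outcome", using baseline and follow-up rows with random intercepts for site and participant. On the test it says: "The null hypothesis of no significant group-by-time interaction at the follow-ups can be tested". It writes out a logit version for MOUD use. It describes ICV in two ways: as a time-varying exposure in the text before the equation, and as an indicator of being at an ICV site in the definitions below it.

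**The concern.** Entry on 4 or more injecting days in the last 30 lies inside the 6-month window of the endpoint, so that route gives a baseline score of 1 by definition. The sharing route has the same 6-month window, and the rubric places people who are not injecting in its no-sharing category, so that route gives a 1 in practice. The exceptions are narrow: someone who only passed on a needle, inconsistent self-report, or a baseline visit held later than screening.

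In the HIV-negative part of the cohort the baseline outcome is thus essentially constant. In the whole cohort, the baseline log odds reflects how many HIV-positive non-injectors each arm happened to recruit. An interaction test with a free baseline arm term subtracts that quantity from the follow-up contrast. Because sites are randomized, the expected baseline difference is zero, so the subtraction brings almost no information on injecting. It does bring the large sampling error of a log odds estimated from very few zeros. What is at stake is the ability to detect a real effect on injecting.

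**Working it through.** **The plan's own figure.** Section 12.4 states 80% power for the composite at 0.33 SD with 720 enrolled and 80% retention. Retained per arm: 360 × 0.8 = 288. For a baseline-to-follow-up change with residual SD 1 and two-sided 5% (both assumed, as neither is stated), the standard error is √2 × √(2/288) = 0.118. Then 0.33/0.118 = 2.80, and power is Φ(2.80 − 1.96) = 0.80. The figure reproduces, but it concerns the continuous composite. No power is given for the injecting endpoint.

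**Possible baseline zeros.** Let h be the HIV-positive share and f the share of HIV-positive participants with no injecting in 6 months. Neither is in the documents. Expected zeros = 720 × h × f:
- h 5%, f 10%: 3.6
- h 10%, f 25%: 18
- h 20%, f 50%: 72
- h 30%, f 50%: 108

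**Hand check with 36 zeros (18 per arm).** The variance of the baseline log odds ratio is 2 × (1/18 + 1/342) = 0.117. At follow-up, with 288 per arm and about 20% not injecting, it is 2 × (1/58 + 1/230) = 0.043. Ignoring within-person correlation, the interaction variance is 0.117 + 0.043 = 0.160, or 3.7 times the follow-up variance. Former injectors tend to be zeros at both visits, and allowing for this lowers the ratio to about 2.6 to 3.1 in simulation.

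**Simulation.** Assumptions, none from the documents: 15% of control baseline injectors have stopped by follow-up, a true odds ratio of 2 for stopping, 20% of former injectors resume, and no site effect. Retention is 80%, with 3000 runs per setting and a person-level robust variance. The last column is a check with a person-random-intercept logistic model and likelihood-ratio test (120 runs, no site intercept, so Monte Carlo standard error up to √(0.25/120) = 4.6 points).

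| Expected zeros of 720 | Variance ratio, interaction to follow-up contrast (OR 1; OR 2) | Power, interaction | Power, follow-up contrast | Random-intercept check |
|---|---|---|---|---|
| 9 | 10.4; 13.1 | 14% | 90% | 25% vs 92% |
| 18 | 5.4; 6.5 | 26% | 88% | 37% vs 88% |
| 36 (h 20%, f 25%) | 2.7; 2.9 | 41% | 85% | 51% vs 87% |
| 72 | 1.5; 1.7 | 55% | 78% | 56% vs 74% |
| 108 | 1.2; 1.3 | 57% | 70% | not run |

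The row with 18 zeros can be checked by hand. The simulated SD of the interaction is 0.531, so ln 2/0.531 = 1.31 and Φ(1.31 − 1.96) = 0.26. With 3.6 expected zeros, the interaction could not be estimated in about 30% of runs, mainly because an arm had no baseline zero.

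**Is the test biased?** With no true effect, the interaction test rejected in at most 5.4% of runs in these settings. A separate null simulation let HIV prevalence vary between sites (10-20%, logit SD 0.3-0.5, 30-50% not injecting, 20% relapse). The mean interaction log odds ratio lay between −0.008 and +0.008. Type I error was 4-5% with variance clustered by site and 5-11% with variance clustered only by person.

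**The case against.** Four points on the other side carry weight.

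- **The weakness depends on which ICV definition is used.** Sections 7.2 and 12.6 have cohorts recruited before allocation is released, or nearly so. A time-varying ICV would then be 0 at almost every baseline visit. ICV and its interaction with follow-up become the same column, and the one estimable coefficient is a follow-up contrast with a common baseline, which largely avoids the problem. This stands, and it makes the point conditional on the site-arm definition.
- **The model for injecting is inferred.** Section 12.7.1 names MOUD as its dichotomous example and says only that the interaction can be tested. Since it gives all outcomes the same data structure and plans to analyze the components separately, the inference is reasonable, but it remains an inference.
- **The number of baseline zeros is unknown.** The criteria were built to raise HIV-positive enrollment, so it may not be small. At 108 zeros the loss is modest (57% against 70%). Also, only the baseline half of the contrast depends on this subgroup; follow-up zeros can come from anyone.
- **Reach is limited.** This is one of 16 listed secondary endpoints. The planned confounder adjustment might include HIV status, but a main effect alone would not repair the interaction, because the baseline outcome stays constant in HIV-negative participants.

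A reader might go further and infer that chance recruitment creates false effects. With 10 against 20 former injectors among 360 per arm, the baseline odds ratio is (340/20)/(350/10) = 0.49, which would seem to yield an interaction of about 2.1 from identical follow-up. That illustrates spread, not bias: the estimate centers on zero, and test size holds when variance is clustered by site. The 5-11% figure comes from ignoring site clustering; Section 12.7.1 plans site random intercepts but does not state the clustering level of its robust variance.

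A reader might also infer that former injectors should be excluded because they cannot reduce injecting. They can relapse, and preventing relapse lowers injecting, so keeping all participants is a legitimate choice.

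**Conclusion.** The point holds as a loss of precision and power for one secondary endpoint, under the site-arm definition of ICV and the common logit model. Over 9 to 108 baseline zeros, the interaction log odds ratio has about 1.2 to 13 times the variance of a follow-up comparison, and with very few zeros it may not be estimable. The mechanism follows from the entry criteria and the rubric alone. The size rests on assumed HIV prevalence, non-injecting share, cessation and relapse rates, and on simulations simpler than the planned three-level model; the random-intercept check agrees in direction. The documents do not support a claim of bias, or of a problem in the composite: in a linear model, an item fixed at 1 at baseline creates no unstable odds.

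**What to change.** For the injecting endpoint, do not test the interaction with a free baseline arm term. Compare arms on any injecting in the prior 6 months at the 7-month visit in all participants, or fit a model constrained to a common baseline. Include a site random intercept and adjust for HIV status and for baseline injecting status or frequency. Report the comparison among baseline injectors as supporting; that subgroup is fixed by pre-intervention data. The objective and its all-participant denominator can stay as they are.

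In Section 12.7.1, reconcile the time-varying and site-arm definitions of ICV, since the former already gives approximately this contrast, and state the level at which the robust variance is clustered. Enrollment is complete (Section 9.3.4), so the number of baseline zeros per arm can be counted and reported.

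The cost is a different model for one secondary endpoint and slightly more analysis work. No new data are needed.
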